lateral classification (Ikuta) subtype P	Fracture occurring proximal to the attachment site of the iliofemoral ligament in which the proximal fragment is displaced posteriorly on an X-ray image.
AP3xML3 classification	Classification of postoperative reduction in which anteroposterior (AP) and mediolateral (ML) X-ray images are each classified into three types. Anteroposterior images are classified as medial, anatomical, or lateral while ML images are classified as intramedullary, anatomical, or extramedullary; the combination of these two classifications results in a total of nine types of reduction.
Sliding	Migration of lag screws caused by loading.
TAD	Tip Apex Distance
Wiper motion	Displacement of the tip of nails within the medullary canal.
EC	Ethical committee
ITT	Intention to treat
IQR	Interquartile range
(S)AE	(Serious) Adverse Event
(S)ADE	(Serious) Adverse Device Event
SPONSOR	The sponsor is the party that commissions the organisation or performance of the research, for example a pharmaceutical company, academic hospital, scientific organisation or investigator. A party that provides funding for a study but does not commission it is not regarded as the sponsor, but referred to as a subsidising party
USADE	Unanticipated Serious Adverse Device Event

SUMMARY

STUDY TITLE	Randomized controlled study comparing Zimmer Natural Nail System Cephalomedullary Asia Nail with Anterior Support Screw (ASS) versus Conventional technique
DESIGN	Prospective, two arm, randomized, controlled, multi-center
OBJECTIVE	Determine the effectiveness of the ASS in terms of ZNN CM Asia with ASS provides better fixation compared to conventional technique
OUTCOME MEASURES	Patient demographic, Operative data, CT assessment, Walking ability, Adverse event
NUMBER OF CASES	Total 240 legs(1 group 120 legs) in Japanese patient population at maximum 15 sites
ELIGIBILITY	Patient who presented with primary trochanteric fracture, has 3-part B or 4-part fracture by 3D-CTclassification (Nakano) and subtype P by lateral classification (Ikuta)
DURATION	Enrolment: 18months Follow-up: Preop, Operation, Immediate postop, 3weeks, 16week Enrolment period: 18 Months Central CT assessment: Postop 3 week Total study duration: 22Months

1. INTRODUCTION

1.1 BACKGROUND

In 2007, the portion of Japanese adults aged 65 years or older reached 21.5% of the total population; Japan has entered into a super-aging society. The percentage of elderly people is estimated to increase continuously¹. The number of proximal femur fracture cases in 2007 in Japan was approximately 150,000 and this would be estimated increasing to 320,000 cases in 2040². For these patients, there are a number of implants present in the market, and orthopaedic physicians are still keeping finding better practice to lessen postoperative complications in patients. The general features of Asian patients are anterior bow radius, high bending point, and short transition length. Achieving appropriate fixation and bony support is important in treatment of trochanteric fracture. Optimal positioning of a nail suitable for bone morphology of the Asian patients may be helpful for further reducing the incidence of postoperative complications.

The Zimmer Natural Nail System Cephalomedially Asia Nail (ZNN CM Asia Nail) which was developed for Asian patients has been selling in January 2013 in Japan. While previous multi-center studies³ demonstrated the suitability of the device for the bone morphology of Japanese patients, displacement of bone fragments occurring in the early postoperative period remains a problem in treatment of trochanteric fracture with the ZNN CM Asia Nail. Fukuda et al. noted re-displacement of fracture resulting in lateral classification subtype P two weeks after surgery in 14% of patients in whom anatomical reduction was achieved immediately after surgery as confirmed by the lateral view⁴. A relatively large number of patients experiencing re-displacement are reported to have significant posterior-lateral displacement of bone fragments at the time of injury, which lead to lack of bony support posteriorly. Many researchers believe that it is desirable to have anterior-medial bony support for these patients. Maehara et al. proposed an adjunctive procedure of anterior support screw (ASS) placement which uses an additional cannulated cancellous screw anteriorly to the lag screw in order to achieve better support⁵. In ASS placement, a screw is inserted just below the anterior cortex, which is called screw augmentation technique. This prevents rotational displacement of bone fragments and may prevent the proximal reduced fragment from re-displacement. The procedure can be performed with the ZNN CM Asia Nail and standard surgical instruments without need of any special instruments.

The present study was designed to evaluate the impact of ASS's on maintenance of postoperative reduction when used in combination with the ZNN CM Asia Nail in Japanese patients who had closed trochanteric fracture.

[figure not shown]

Fig1. Screw Augmentation Technique

1.2 DEVICE / IMPLANT DESCRIPTION

The devices used in this study are as follows:

- ZNN CM Asia Nail
- ZNN CM Lag Screw
- ZNN CM locking screw
- ZNN CM Nail Cap

All implants are made from titan alloy. With ASS group, ACE 4.5/5mm Cannulated Cortical Lag Screw 20mm

Thread which made from titan alloy can be used.

Fig 2. ZNN CM Asia Nail with ASS

1.3 RATIONALE AND PURPOSE FOR CURRENT STUDY

The purpose of this study is to compare post-operative 3weeks fracture reduction maintenance rate between patients operated with ASS (investigational group) and patients operated without ASS (Control group) using same implant system (ZNN CM Asia, Zimmer Biomet).

2. STUDY DESIGN

This Study is a prospective, randomized, multicentre study, comparing the clinical outcomes ZNN CM Asia with the use of ASS versus ZNN CM Asia without ASS. A total 240 subjects will be recruited prospectively and randomized (enveloped method) according to a 1:1 scheme.

2.1 STUDY GROUPS/ TREATMENTS

Patients will be included that their trochanteric fracture classification is 3-partB or 4-part in 3D-CT classification (Nakano) with subtype P in lateral classification (Ikuta).

There will be two study groups with each 120 patients. Patients will be assigned to the investigational or the control group using 1:1 randomization. In the investigational group, patients will be treated in ZNN CM Asia with ASS technique. Patients in the control group will be treated in ZNN CM Asia with conventional technique.

Group 1 “Investigational”: Patients receiving a ZNN CM Asia with ASS technique.

Group 2 “Conventional Signature”: Patients receiving a ZNN CM Asia without ASS (conventional) technique.

2.2 NUMBER OF SITES AND SUBJECTS/PROCEDURES

240 cases will be enrolled and randomly assigned to either the investigational or the control group. This study will be conducted at maximum 15 Japanese hospitals.

The enrolment limit of 1 site is 48cases (20% of total enrolment) for well distribution between sites.

2.3 PRIMARY AND SECONDARY ENDPOINTS

Primary Endpoint

The maintenance rate of immediate post-operative reduction position versus 3 week post-operative Re-displacement (Lateral reduction classification⁶):

- SubtypeP: Femoral head fragment fall down into diaphysis medullary space.
- SubtypeN: Even a little contact between femoral head fragment and anterior cortical bone.
- SubtypeA: Femoral head fragment located outside of medullary space..

[figure not shown]

Fig.3 Lateral reduction classification

Secondary Endpoint

- Surgery time
- Post-operative reduction position (AP3xML3)
- Pre-operative fracture classification and with or without open reduction
- CT assessment
- Safety evaluation

2.4 ASSESSMENT PROCEDURE

The study assessment period will be 22 months, 18 months recruitment and 16 months follow-up. The follow-up for all patients will be at the following time points: baseline (preoperative), surgery, 3 weeks (+/- 3days) and 16 weeks (+/- 4 weeks)*.

*16 weeks assessment is optional item

A. Preoperative:

- a. Informed Consent
- b. Randomization
- c. Historical Record
- d. Fracture Classification (CT/X-ray)

B. Operative:

- a. Operative Form
 - i. Reduction (Open/ Closed)
 - ii. Surgery Time (reduction, from skin incision to closure)
 - iii. Implant Component Information (include diameter of sizer reamer)

C. Immediate postoperative and 3 week:

- a. CT Assessment
- b. Fracture Classification (If patient have not taken preoperative CT assessment)

D. 16 week (optional):

- a. CT Assessment
- b. Walking Ability

2.5 ASSESSMENT PARAMETERS AND METHODS

Preoperative data

After the patient has been consented he/she will be assigned randomly to either the investigational or control group. Demographic information will be collected, a detailed medical history will be obtained and a physical examination will be performed (including height and weight).

Clinical Assessment (optional assessment for 16 week)

Walking ability is optional item to assess the difference between investigational and control group.

Operative

The target reduction position is type Anterior (A), using suitable Nail size for medullary diameter.

CT Assessment

At immediate postoperative, 3 weeks and 16 weeks (optional) follow-up visit, femur CT images will be taken. In the CT images, patient personal information will be deleted and assessed comparison between immediate-postop and 3weeks postop, and additional 16 weeks evaluation by central CT reviewer. CT imagine assessment is consist of Reduction Position, Sliding Length of Lag Screw, TAD, Tip position of Nail (including wiper motion) and Medullary Canal Occupation Rate.

Postoperative therapy

Each patient is permitted full load as soon as possible depending on their pain.

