2.6 ASSESSMENT TIMELINE/ SCHEDULE

Each follow-up visit time point will be determined based on the date of surgery. Each follow-up visit has a specific allowed time window:

- Preoperative
- Immediate Postoperative (after surgery within 3days)
- 3weeks (+/-3days)
- 16weeks* (-4weeks) *optional assessment

In the table below the retrieved information is per follow-up visit is found.

Assessment	Preop	Operative	3days	3weeks +/-3days	16weeks (- 4weeks)
Informed Consent	X				
Randomization	X				
Historical Record	X				

Operative Record		X			
Fracture type [CT/X-ray]	X		(X) ^{*1}		
CT assessment	(X)		X	X	(X)
Walking ability	(X) ^{*2}				(X)
Complications		As needed			

- () is optional assessment item.
- ^{*1} In the case of classified in X-ray in preoperative, reclassify the fracture type in postoperative CT.
- ^{*2} In the case of asking questionnaire impossibility, ask their preinjury walking ability in postoperative.

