7. STATISTICAL ANALYSIS PLAN

7.1 SAMPLE SIZE CALICULATION

The primary analysis for the study will compare the maintenance rate of immediate post-operative reduction position on the 3 week post-operative x-ray for Investigational (with ASS technique) vs. Control (without ASS technique). Sample size calculations for this study are done using data found in a paper by Maehara et al⁵. In this study, 87.5% of the patients with ASS technique were maintaining immediate post-operative reduction position, as compared to 72.7% in the conventional cohort. Our sample size calculation assumes the result in this study will be similar to what is reported in Maehara et al.

The null hypothesis is that the maintenance rate of immediate post-operative reduction position for the investigational group (with ASS technique) is less than or equal to that of the patients operated without ASS technique. The alternative hypothesis is the maintenance rate of immediate post-operative reduction position for the investigational group (with ASS technique) is greater than that of the patients operated without ASS technique.

Null Hypothesis : $H_0: \pi_A - \pi_B \leq 0$

Alternative Hypothesis : $H_A: \pi_A - \pi_B > 0$

Where π_A represents the maintenance rate of immediate post-operative reduction position in investigational group on the 3 weeks postoperative CT and π_B represents the maintenance rate of immediate post-operative reduction position in control group on the 3 weeks postoperative CT.

If we reject the null hypothesis, we can conclude that the ZMM CM Asia with ASS technique is superior to the conventional technique in trochanteric fracture with regard to the maintenance rate of immediate post-operative reduction position.

The sample size calculation was conducted anticipating the use of a Pearson's Chi-square test.

Alpha level: 5% (two sided)

Power: 80%

Investigational group maintenance rate for reduction position: 87.5%

Control group maintenance rate for reduction position: 72.7%

The resulting calculation gives $n=113$ per group. 120 patients per group will allow for up to 5% attrition.

Overall population per protocol: 240

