7.4 DATA ANALYSES

Data will be analysed using SAS 9.0 or higher. The Type I error rate for the primary study analysis will be 0.05. Comparisons for secondary, exploratory, and safety analyses will be two-sided comparisons using $\alpha = 0.05$, with no adjustment for multiple comparisons.

Primary Analysis: The primary analysis will be performed on the set of patients with non-missing CT data at 3 weeks (Full Analysis Set (FAS)). Sensitivity analyses will be presented for the intention-to-treat (ITT) patient group. A two-tailed Pearson’s Chi-Square test at $\alpha = 0.05$ will be used to assess the study hypotheses and determine whether there is a statistically significant difference between investigational and control groups with regard to the maintenance rate of immediate post-operative reduction position.

Secondary Analysis: Analyses for secondary endpoints will be on the FAS, and will only use those cases with complete data for the endpoint being analysed.

Continuous data (e.g. age, BMI) will be reported using mean, standard deviation, median, and range. Comparisons between Investigational vs Control groups with regard to continuous baseline and secondary outcomes will be performed using standard statistical tests and will be chosen as appropriate for the scale and distribution of the measures being analyzed. For example, a t-test, Wilcoxon test, or one-way ANOVA (as appropriate) may be performed to assess differences in means/medians.

Categorical data (e.g. gender, classification of fracture) will be reported using frequency and percentage. Comparisons of Investigational vs Control with regard to categorical baseline, secondary and safety outcomes will be performed using standard statistical tests and will be chosen as appropriate for the scale and distribution of the measures being analyzed. For example, categorical outcomes may be compared for investigational and control groups using the Pearson’s chi-square test.

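### Week-16 walking ability is meant to compare the arms and an optional pre-injury value is scheduled, but the plan gives that value no role in the analysis; a prespecified adjusted model would be more precise.

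*Combined protocol and SAP*

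**What the plan says.** The summary lists walking ability among the outcome measures, and 2.5 gives it a comparative purpose: "Walking ability is optional item to assess the difference between investigational and control group". It does not appear among the secondary endpoints in 2.3, and no section defines the scale.

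The table in 2.6 schedules walking ability twice, preoperatively and at week 16. Both entries are in brackets, which the table's key defines as optional. A footnote covers patients who cannot answer the questionnaire before surgery; for them the site is to "ask their preinjury walking ability in postoperative". The preoperative list in 2.4A does not include the item.

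For continuous baseline and secondary outcomes, 7.4 leaves the test to be chosen according to the measure, and says by way of example that "a t-test, Wilcoxon test, or one-way ANOVA (as appropriate) may be performed to assess differences in means/medians". For categorical outcomes the example is Pearson's chi-square. Secondary analyses use only cases with complete data for the endpoint in question. No section names a covariate, a change from pre-injury level, or a regression model for walking ability.

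**The concern.** The plan schedules a baseline for an outcome that it intends to compare between arms, and then says nothing about using it. If pre-injury ability predicts walking at week 16, a comparison that ignores it has a wider confidence interval than necessary and leaves any chance imbalance in pre-injury level uncorrected. The week-16 visit is optional, so the number observed may fall well below 120 per arm. Precision is then scarcer and chance imbalance more likely.

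Timing also matters if the value is to serve as a covariate. An answer recalled after surgery is obtained after randomisation and treatment. Section 2.5 mentions random assignment straight after consent and data collection only after that, so even a preoperative answer could follow allocation. No blinding of patients or site staff is described; only the CT images are stripped of patient information for central reading.

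**Working it through.** **The plan's own figure.** The only sample-size figure is for the primary endpoint: "The resulting calculation gives $n=113$ per group". Inputs from 7.1: rates 0.875 and 0.727, two-sided alpha 5%, power 80%. With pooled variance under the null and mean rate 0.801:

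- n = [1.960 × sqrt(2 × 0.801 × 0.199) + 0.842 × sqrt(0.727 × 0.273 + 0.875 × 0.125)]² / 0.148² = 113.05.
- Rounded up this is 114; at 113 per group the power is 79.98%. The stated figure reproduces.
- Attrition: 113 / 0.95 = 118.9, and 120 × 0.95 = 114, so 120 per group is consistent.

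None of this concerns walking ability, for which the documents give no correlation, standard deviation (SD), scale or expected number observed.

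**Gain from adjustment (assumed r, linear model).** Adjusting for a baseline with correlation r multiplies the variance of the arm difference by 1 − r². The detectable difference at 80% power (two-sided 5%) is 2.80 × sqrt(2/n) SD unadjusted, and that times sqrt(1 − r²) adjusted. Two cases are shown: 114 per arm (120 less 5%) and 60 per arm (assumed, because the visit is optional).

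| r | Variance cut | Interval narrower by | Detectable, 114 per arm (unadjusted 0.371 SD) | Detectable, 60 per arm (unadjusted 0.511 SD) |
|---|---|---|---|---|
| 0.3 | 9% | 4.6% | 0.354 SD | 0.488 SD |
| 0.5 | 25% | 13.4% | 0.321 SD | 0.443 SD |
| 0.7 | 49% | 28.6% | 0.265 SD | 0.365 SD |

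In patient numbers, 114 per arm with adjustment is worth 114 / (1 − r²) = 125, 152 or 224 per arm without it. An effect with 80% power unadjusted has 83.6%, 89.9% or 97.5% power adjusted.

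**Check on an ordinal scale.** Simulation with an assumed five-level scale, 114 per arm and a latent shift of 0.38 SD (3,000 runs) gave this power:

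| Latent r | Wilcoxon | t-test | ANCOVA |
|---|---|---|---|
| 0.3 | 77% | 78% | 81% |
| 0.5 | 77% | 78% | 87% |
| 0.7 | 78% | 78% | 95% |

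Type I error was 4.5% to 5.9% throughout (2,000 runs each).

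**Effect of missing pre-injury values.** Let f be the share of week-16 patients who have the value, with missingness unrelated to arm or outcome.

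- If the others are dropped, the variance relative to the unadjusted analysis is (1 − r²) / f. This is below 1 only when f exceeds 1 − r²: 91%, 75% or 51% at r of 0.3, 0.5 or 0.7.
- If they are kept with a single imputed value common to both arms, the ratio is f(1 − r²) + (1 − f) = 1 − f r².
- Example with f = 0.75 and r = 0.5: dropping gives 0.75 / 0.75 = 1.00, no gain. Keeping gives 1 − 0.75 × 0.25 = 0.81, a cut of about 19%.

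The full cut of r² therefore needs the value for everyone. With a rule that keeps all patients, part of the gain survives missingness.

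**The case against.** Several stronger readings are tempting, and the documents do not support them.

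- A reader might infer that the pre-injury value is collected on everyone and then ignored. It is bracketed as optional, like the week-16 item, so either can be missing.
- A reader might infer that 7.4 prescribes unadjusted tests. They are examples, the choice is left open, and an adjusted model is not ruled out. Since walking ability is not a listed secondary endpoint, it is not even clear that the secondary-analysis rules govern it. What is missing is prespecification.
- A reader might infer that adjustment is free. With an optional baseline and no rule for missing values, a fitted ANCOVA drops patients and can lose precision, as shown above. On the other side, the complete-case rule in 7.4 refers to the endpoint, so it does not itself require excluding patients who lack only a covariate.
- A reader might infer that post-operative recall is the normal route, or that the arm is known when the question is asked. Recall is already a fallback for patients who could not be questioned before surgery, and no section says who asks or whether patients are told their arm. The absence from 2.4A is weak evidence of a fault: the optional preoperative CT assessment is absent there too.

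The strongest objection is that unadjusted comparison of randomised arms is valid, the item is optional, and the size of the gain rests wholly on assumptions. All of that stands. At r = 0.3 the gain is small. It limits the weight of the point without removing it: no use of the pre-injury value is planned, and an adjusted model chosen after the data are seen is less credible than one fixed in advance.

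**Conclusion.** The point holds as a matter of efficiency and prespecification. The plan intends a between-arm comparison of week-16 walking ability, schedules an optional pre-injury value, and gives that value no analytic role. The cost is a confidence interval wider by an amount that the documents do not fix. It is minor at low correlation and substantial at r of 0.5 or above, provided patients without a pre-injury value are kept. The SD-based figures assume a linear model and do not carry over directly to a proportional-odds model.

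Nothing here makes the unadjusted comparison biased or invalid, and nothing touches the primary test, its sample size or the trial's main conclusion. It is a desirable improvement to an optional outcome.

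**What to change.** 1. In 7.4, analyse week-16 walking ability with a model containing arm and pre-injury walking ability: ANCOVA, or proportional odds if the scale is ordinal. Report the adjusted estimate with its 95% confidence interval.
2. State a rule that keeps patients with a missing pre-injury value, for example single imputation blind to arm, or a missing indicator.
3. Define the walking-ability scale and its endpoint status, since the choice of model depends on the scale.
4. Add the pre-injury question to 2.4A, asked at consent before the envelope is opened where possible. Flag values recalled after surgery so that their influence can be examined.

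Cost: a few sentences of text, and one question recorded routinely before randomisation that is now optional. No new visits or patients are needed, and the primary analysis and sample size stay as they are.

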2.6 ASSESSMENT TIMELINE/ SCHEDULE

Each follow-up visit time point will be determined based on the date of surgery. Each follow-up visit has a specific allowed time window:

- Preoperative
- Immediate Postoperative (after surgery within 3days)
- 3weeks (+/-3days)
- 16weeks* (-4weeks) *optional assessment

In the table below the retrieved information is per follow-up visit is found.

Assessment	Preop	Operative	3days	3weeks +/-3days	16weeks (- 4weeks)
Informed Consent	X				
Randomization	X				
Historical Record	X				

Operative Record		X			
Fracture type [CT/X-ray]	X		(X) ^{*1}		
CT assessment	(X)		X	X	(X)
Walking ability	(X) ^{*2}				(X)
Complications		As needed			

- () is optional assessment item.
- ^{*1} In the case of classified in X-ray in preoperative, reclassify the fracture type in postoperative CT.
- ^{*2} In the case of asking questionnaire impossibility, ask their preinjury walking ability in postoperative.

